2 SCHEDULE OF ACTIVITIES

Study assessments and procedures are presented in [Table 2-1](#) (Screening Procedural Outline), [Table 2-2](#) (On Treatment Procedural Outline), and [Table 2-3](#) (Long-term Follow-up Procedural Outline).

In the event that multiple procedures are required at a single time point, the electrocardiogram (ECG) may be obtained up to 15 minutes earlier, vital signs may be obtained up to 10 minutes earlier or later, and clinical laboratory samples may be obtained up to 5 minutes earlier than the nominal time point, ensuring that the pharmacokinetic (PK) samples can be collected on time.

Table 2-1: Screening Procedural Outline (CA020016)

Procedure	Screening Visit (Day -28 to -1)	Screening Visit (Day -14 to -1)	Notes ^a
Eligibility Assessments			
Informed Consent	X		Must be obtained prior to performing any screening procedures. A participant is considered enrolled only when a protocol-specific informed consent is signed. Study allows for re-enrollment of a participant who has discontinued the study as a pretreatment failure. If re-enrolled, the participant must be re-consented and assigned a new participant number from IRT.
Contact IRT	X		Register in IRT to obtain participant number.
Inclusion/Exclusion Criteria	X		Must be confirmed prior to randomization.
Medical History	X		All medical history relevant to disease under study.
Safety Assessments			
PE, Measurements, Vital Signs, and PS		X	Includes height, weight, BMI, PS (see Appendix 7), seated BP, heart rate, temperature and oxygen status by pulse oximetry. BP and heart rate should be measured after the participant has been resting quietly for at least 5 minutes. Must be collected within 14 days prior to randomization.
Assessment of Signs and Symptoms		X	Within 14 days prior to randomization.
Concomitant Medication Collection		X	Within 14 days prior to randomization. Vaccine use within 30 days prior to first study intervention.
ECG		X	At rest. Within 14 days prior to randomization. ECGs should be recorded after the participant has been supine for at least 5 minutes, and prior to blood draws.
AE and SAE Assessment	X		All SAEs must be collected from the date of participant's written consent. All AEs (SAEs or non-serious AEs) associated with SARS-CoV-2 infection collected from time of consent.

Table 2-1: Screening Procedural Outline (CA020016)

Procedure	Screening Visit (Day -28 to -1)	Screening Visit (Day -14 to -1)	Notes ^a
Laboratory Tests			
Clinical Laboratory Assessments	X	X	Day -14 to -1: On-site/local laboratory tests must be performed within 14 days prior to randomization. Day -28 to -1: Viral testing to be completed within 28 days prior to randomization. For HIV: testing at sites where locally mandated. Refer to Section 9.4.4 for list of laboratory tests to conduct.
Pregnancy Test (WOCBP only)		X	Serum or urine pregnancy test (minimum sensitivity equivalent units 25 IU/L or equivalent units of HCG) to be done at screening visit and repeated within 24 hours prior to first dose of study intervention.
FSH		X	FSH screening - only required to confirm menopause in women < 55 years of age.
Biomarker Assessments			
Tumor Sample	X		A FFPE tumor tissue block (preferred, equivalent to 20 sections) or a minimum of 20 unstained slides* of tumor tissue obtained during screening or prior to enrollment (within 3 months of enrollment and with no intervening systemic anti-cancer treatment between time of acquisition and enrollment) must be sent to the central laboratory prior to randomization. Samples may be from core biopsy, punch biopsy, excisional biopsy or surgical specimen. Fine needle aspirates or other cytology samples are NOT acceptable. Prior to randomization, central laboratory must provide IRT with assessment of tumor-cell PD-L1 expression by IHC using pre-treatment tissue sample as described in the Laboratory Manual. *If despite best efforts, a minimum of 20 slides is not obtainable, submission of fewer slides may be acceptable in some circumstances following discussion with Sponsor or designee. Please refer to Section 9.8 for additional information.

Table 2-1: Screening Procedural Outline (CA020016)

Procedure	Screening Visit (Day -28 to -1)	Screening Visit (Day -14 to -1)	Notes ^a
EGFR, ALK, ROS-1, KRAS, and BRAF V600E Mutation Status	X		
EGFR, ALK, and ROS-1 results required for all nonsquamous participants prior to randomization. Historical results obtained as standard of care prior to screening period are acceptable. EGFR mutation, ALK, and ROS-1 tests should be performed by site. The use of FDA-approved or local Health Authority tests for EGFR and ALK are strongly encouraged.
 
 EGFR mutation test (tumor tissue or blood) will be performed using PCR-based assay or next generation sequencing. Tests other than PCR or next generation sequencing will be requested to be repeated using PCR or next generation sequencing-based methods. ALK translocations and ROS-1 rearrangement tests are mandatory for participants with nonsquamous histology. Participants with known ALK translocations/ROS-1 rearrangements which are sensitive to available targeted inhibitor therapy are excluded. If known status of BRAF V600E mutations (which are sensitive to available targeted inhibitor), participant is excluded. If BRAF mutation status is unknown or indeterminate, participant may enroll. If known, KRAS mutation status should be documented for all participants.
Biomarker Sample Collections	Refer to biomarker collection table in Section 9.8 for timing of collections.		
Tumor Assessments			
Body Imaging	X		Contrast enhanced CT of the chest, CT/MRI of the abdomen, pelvis, and all other known and/or suspected sites of disease, within 28 days prior to randomization. See Section 9.1.1.1 for further details.
Brain Imaging	X		MRI of the brain (without and with contrast) is required for ALL participants during screening to rule out brain metastases, within 28 days prior to randomization. CT of the brain (without and with contrast) can be performed if MRI is contraindicated. See Section 9.1.1.1 for further details.

Abbreviations: AE, adverse event; ALK, anaplastic lymphoma kinase; BMI, body mass index; BP, blood pressure; BRAF, b-rapidly accelerated fibrosarcoma proto-oncogene; CRF, case report form; CT, computed tomography; ECG, electrocardiogram; EGFR, epidermal growth factor receptor; FDA, Food and Drug Administration; FFPE, formalin-fixed paraffin-embedded; FSH, follicle-stimulating hormone; HCG, human chorionic gonadotropin; HIV, human immunodeficiency virus; IHC, immunohistochemistry; IRT, interactive response technology; KRAS, Kirsten rat sarcoma viral oncogene homolog; MRI, magnetic resonance imaging; PCR, polymerase chain reaction; PD-L1, programmed death-ligand 1; PE, physical examination; PS, performance status; ROS-1, c-ros oncogene 1; SAE, severe adverse event; SARS-CoV-2, severe acute respiratory syndrome coronavirus 2; WOCBP, women of childbearing potential.

^a Some of the assessments referred to in this section may not be captured as data in the CRF. They are intended to be used as safety monitoring by the treating physician. Additional testing or assessments may be performed as clinically necessary or where required by institutional or local regulations.

Table 2-2: On Treatment Procedural Outline (CA020016)

Procedure	Cycle 1 ^a Visit Window = -3 Days for C1D1, ± 3 Days for All Others					Each Subsequent Cycle		EOT	Notes ^b 1 Cycle = 6 Weeks
	D1	D8	D15	D22	D29	D1 (± 3 Days)	D22 (± 3 Days)		
Safety Assessments									
Complete PE, Vital Signs, Physical Measurements, and PS	X						X	X	Includes weight, BMI, heart rate, seated BP, temperature, oxygen saturation by pulse oximetry and PS (see Appendix 7). BP and heart rate should be measured after the participant has been resting quietly for at least 5 minutes.
Targeted PE, Vital Signs, Physical Measurements, and PS		X	X	X	X			X	Includes weight, BMI, heart rate, seated BP, temperature, oxygen saturation and PS (see Appendix 7). BP and heart rate should be measured after the participant has been resting quietly for at least 5 minutes.
ECGs	X						X	X	ECGs should be recorded after the participant has been supine for at least 5 minutes, and prior to blood draws.
Concomitant Medication Use	Continuously during the study							X	Record at each visit
AE and SAE Assessment	Continuously during the study							X	Record at each visit. All AEs (SAEs or non-serious AEs), including those associated with SARS-CoV-2 infection, must be collected continuously during the treatment period. For reporting purposes, all AEs/SAEs must be graded using CTCAE v5. All SAEs must be collected from the date of participant's written consent until 100 days post discontinuation of dosing.

Table 2-2: On Treatment Procedural Outline (CA020016)

Procedure	Cycle 1 ^a Visit Window = -3 Days for C1D1, ± 3 Days for All Others					Each Subsequent Cycle		EOT	Notes ^b 1 Cycle = 6 Weeks
	D1	D8	D15	D22	D29	D1 (± 3 Days)	D22 (± 3 Days)		
Laboratory Tests									
Clinical Laboratory Assessments	X			X		X	X	X	Perform on site/local laboratory testing within 72 hours prior to each dose. For the first treatment visit, labs need not be repeated if they were performed within 72 hours and the results are available and have been reviewed for eligibility. Refer to Section 9.4.4 for the list of laboratory tests to be conducted.
Pregnancy Test (WOCBP only)	X			X		X	X	X	Serum or urine within 24 hours prior to first dose, and then every 3 weeks regardless of dosing schedule.
PK and Immunogenicity Assessments									
PK and Immunogenicity Collections	Refer to PK/Immunogenicity collection table in Section 9.5 for timing of collections								
Biomarker Assessments									
Tumor Biopsy					X				Mandatory on-treatment biopsies (if medically feasible) required for all participants. Biopsy window for C1D29 is ± 5 days. EOT/Progression biopsy is optional.
Biomarker Sample Collections	Refer to biomarker collection table in Section 9.8 for timing of collections.								

Table 2-2: On Treatment Procedural Outline (CA020016)

Procedure	Cycle 1 ^a Visit Window = -3 Days for C1D1, ± 3 Days for All Others					Each Subsequent Cycle		EOT	Notes ^b 1 Cycle = 6 Weeks
	D1	D8	D15	D22	D29	D1 (± 3 Days)	D22 (± 3 Days)		
Tumor Assessments									
Body Imaging	Contrast enhanced CT of the chest, CT/MRI of the abdomen, pelvis, and all other known and/or suspected sites of disease should occur every 6 weeks (± 7 days) starting from randomization for the first 48 weeks, then every 12 weeks (± 7 days) until BICR confirmed disease progression or treatment discontinuation (including treatment beyond progression), whichever occurs later. See Section 9.1.1.1 for further details.								
Brain Imaging	Participants with a history of brain metastasis or symptoms should have surveillance MRIs (without and with contrast) per standard of care (approximately Q12W) or sooner if clinically indicated. CT of the brain without and with contrast can be performed if MRI is contraindicated. See Section 9.1.1.1 for further details.								
Clinical Outcomes Assessments									
NSCLC-SAQ	X					X		X	Completed electronically prior to dosing on Day 1 of each cycle from Cycle 1 and then every cycle thereafter for the remainder of the treatment period. See Section 9.1.2 for further details.
FACT-G7	X					X		X	
EQ-5D-5L	X					X		X	
PGIS	X					X		X	
PGIC						X		X	Completed electronically prior to dosing on Day 1 of each cycle from Cycle 2 and then every cycle thereafter for the remainder of the treatment period. The PGIC is not administered on C1D1. See Sections 9.1.2 and 9.1.2.4 for further details.

Table 2-2: On Treatment Procedural Outline (CA020016)

Procedure	Cycle 1 ^a Visit Window = -3 Days for C1D1, ± 3 Days for All Others					Each Subsequent Cycle		EOT	Notes ^b 1 Cycle = 6 Weeks
	D1	D8	D15	D22	D29	D1 (± 3 Days)	D22 (± 3 Days)		
Study Intervention									
IRT Randomization	X								Participant must receive the first dose of study medication within 3 calendar days from vial allocation.
BMS-986207 or Placebo	X			X		X	X		BMS-986207 600 mg Q3W. See Sections 5.1.2 and 7.1 for further details. Details of study drug preparation are found in the Pharmacy Manual.
Nivolumab	X			X		X	X		Nivolumab 360 mg Q3W. Participants may be dosed no less than 19 days from the previous dose.
Ipilimumab	X					X			Ipilimumab 1 mg/kg Q6W. Use body weight for dosing calculations. It is not necessary to re-calculate subsequent doses if the participant weight is within 10% of the baseline weight or the weight used to calculate the previous dose. Round all doses to the nearest milligram per institutional standard.

Abbreviations: AE, adverse event; BICR, blinded independent central review; BMI, body mass index; BP, blood pressure; C1D1, cycle 1 day 1; CRF, case report form; CT, computed tomography; CTCAE, Common Terminology Criteria for Adverse Events; D, day; ECG, electrocardiogram; EOT, end of treatment; EQ-5D-5L, 5 Level EQ-5D Questionnaire; FACT-G7, Functional Assessment of Cancer Therapy - General - 7 item version; IgG, immunoglobulin G; IRT, interactive response technology; MRI, magnetic resonance imaging; NSCLC-SAQ, Non Small Cell Lung Cancer Symptom Assessment Questionnaire; PE, physical examination; PGIC, Patient Global Impression of Change; PGIS, Patient Global Impression of Severity; PK, pharmacokinetic; PS, performance status; Q3W, every 3 weeks; Q6W, every 6 weeks; Q12W, every 12 weeks; SAE, severe adverse event; SARS-CoV-2, severe acute respiratory syndrome coronavirus 2; WOCBP, women of childbearing potential.

^a If a dose is delayed, the procedures schedule for that same time point must also be delayed to coincide with when that time point's dosing actually occurs, with the exception of tumor assessments which must occur as scheduled.

^b Some of the assessments referred to in this section may not be captured as data in the CRF. They are intended to be used as safety monitoring by the treating physician. Additional testing or assessments may be performed as clinically necessary or where required by institutional or local regulations.

Table 2-3: Long-term Follow-up Procedural Outline (CA020016)

Procedure	Safety Follow-up (relative to the last dose of study intervention) ^a			Imaging Follow-up (assessed Q12W for 2 years from last dose of study intervention) ^b	Survival Follow-up (assessed Q12W for 4 years from randomization) ^b	Notes ^c
	Follow-up 1 30 Days (± 7 Days)	Follow-up 2 60 Days (± 7 Days)	Follow-up 3 100 Days (± 7 Days)			
Safety Assessments						
Targeted PE, Vital Signs, and PS	X	X	X			Record at each visit.
Concomitant Medication Use	X	X	X			Record at each visit.
AE and SAE Assessment	X	X	X			
All SAEs and non-serious AEs should be collected continuously for a minimum of 100 days following discontinuation of study intervention. Beyond 100 days from the last dose of study therapy, participants will be followed for drug-related AEs/SAEs until resolution, returns to baseline, or is deemed irreversible, or until the participant is lost to follow-up or withdraws study consent.
 
Participants will be followed for all SAEs, non-serious AEs of special interest (as defined in Section 9.2), and all AEs (SAEs and non-serious AEs) associated with confirmed or suspected SARS-CoV-2 infection until resolution, the condition stabilizes, the event is otherwise explained, the event is deemed irreversible, the participant is lost to follow-up (as defined in Section 8.3), or for suspected cases, until SARS-CoV-2 infection is ruled-out.

Table 2-3: Long-term Follow-up Procedural Outline (CA020016)

Procedure	Safety Follow-up (relative to the last dose of study intervention) ^a			Imaging Follow-up (assessed Q12W for 2 years from last dose of study intervention) ^b	Survival Follow-up (assessed Q12W for 4 years from randomization) ^b	Notes ^c
	Follow-up 1 30 Days (± 7 Days)	Follow-up 2 60 Days (± 7 Days)	Follow-up 3 100 Days (± 7 Days)			
Laboratory Tests						
Clinical Laboratory Assessments	X	X	X			Refer to Section 9.4.4 Clinical Safety Laboratory Assessments for the list of laboratory tests.
Pregnancy Test (WOCBP only)	X	X	X			Serum or urine.
Efficacy Assessments						
Survival Status and Subsequent Cancer Therapy	X	X	X		X	Collect every 3 months (12 weeks) in survival visits until death, lost to follow-up, or withdrawal of study consent. May be performed by phone contact or office visit. Additional subsequent cancer therapy details such as regimen, setting of the regimen, line of therapy, start date and end date of each regimen, best response to the regimen, and date of progression after second-line therapy will be collected. During Safety Follow-up (Follow-up Visits 1, 2, and 3) and every 3 months (clinic visit or by telephone) during Survival Follow-up. Include documentation of subsequent cancer therapy (ie, systemic therapy, tumor-directed surgery, or radiation therapy).

Table 2-3: Long-term Follow-up Procedural Outline (CA020016)

Procedure	Safety Follow-up (relative to the last dose of study intervention) ^a			Imaging Follow-up (assessed Q12W for 2 years from last dose of study intervention) ^b	Survival Follow-up (assessed Q12W for 4 years from randomization) ^b	Notes ^c
	Follow-up 1 30 Days (± 7 Days)	Follow-up 2 60 Days (± 7 Days)	Follow-up 3 100 Days (± 7 Days)			
Tumor Assessments						
Body Imaging				X		For participants who have not experienced BICR-confirmed PD radiographic assessments, or who discontinue study intervention for reasons other than PD, contrast-enhanced CT of the chest and CT/MRI of the abdomen, pelvis, and all other known and/or suspected sites of disease should continue Q6W (± 7 days) starting from date of randomization until Week 48, and then Q12W (± 7 days) beginning on Week 49 until BICR confirmed disease progression, death, or withdrawal of consent, whichever occurs first. See Section 9.1.1.1 for further details.
Brain Imaging				X		Participants with a history of brain metastasis or symptoms should have a surveillance MRI (without and with contrast) per standard of care (approximately every 12 weeks), or sooner if clinically indicated. CT of the brain without and with contrast can be performed if MRI is contraindicated. See Section 9.1.1.1 for further details.

Table 2-3: Long-term Follow-up Procedural Outline (CA020016)

Procedure	Safety Follow-up (relative to the last dose of study intervention) ^a			Imaging Follow-up (assessed Q12W for 2 years from last dose of study intervention) ^b	Survival Follow-up (assessed Q12W for 4 years from randomization) ^b	Notes ^c
	Follow-up 1 30 Days (± 7 Days)	Follow-up 2 60 Days (± 7 Days)	Follow-up 3 100 Days (± 7 Days)			
PK and Immunogenicity Assessments	Refer to PK/Immunogenicity collection table in Section 9.5 for timing of collections.					
Biomarker Collection and Assessments	Refer to biomarker collection table in Section 9.8 for timing of collections.					
Clinical Outcome Assessments						
NSCLC-SAQ	X	X	X		X	To be completed electronically at Safety Follow-Up (Visits 1, 2, and 3 after last dose or date of treatment discontinuation) and only during Survival Follow-up beginning every 12 weeks from Follow-up Visit 3 (100 day Safety Follow-up). To be completed prior to any other study procedure. See Section 9.1.2 for further details.
FACT-G7	X	X	X		X	
EQ-5D-5L	X	X	X		X	

Abbreviations: AE, adverse event; BICR, blinded independent central review; CT, computed tomography; D, day; EQ-5D-5L, 5 Level EQ-5D Questionnaire; FACT-G7, Functional Assessment of Cancer Therapy - General - 7 item version; IgG, immunoglobulin G; MRI, magnetic resonance imaging; NSCLC-SAQ, Non Small Cell Lung Cancer Symptom Assessment Questionnaire; PD, progressive disease; PE, physical examination; PK, pharmacokinetic; PS, performance status; Q6W, every 6 weeks; Q12W, every 12 weeks; SAE, severe adverse event; SARS-CoV-2, severe acute respiratory syndrome coronavirus 2; WOCBP, women of childbearing potential.

^a Participants must be followed for at least 100 days after last dose of study intervention. Follow-Up Visit 1 must occur 30 days from the last dose (± 7 days) or can be performed on the date of discontinuation if that date is greater than 30 days after last dose. Follow-up Visits 2 and 3 occur approximately 60 and 100 days (± 7 days) from last dose of study medication.

- b Survival follow-up visits to occur every 3 months (12 weeks) (\pm 14 days) from the date of randomization. Survival follow-up assessments may be conducted in clinic or by telephone. BMS may request that survival data be collected on all treated participants outside of the 3 month specified window. At the time of this request, each participant will be contacted to determine their survival status unless the participant has withdrawn consent for all contact.
- c Some of the assessments referred to in this section may not be captured as data in the CRF. They are intended to be used as safety monitoring by the treating physician. Additional testing or assessments may be performed as clinically necessary or where required by institutional or local regulations.

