BMS-986207 or its placebo will always be given as the last treatment after nivolumab and/or ipilimumab. Thus, an approximately 30-minute infusion of nivolumab will be followed by a 30-minute observation period, followed by a 30-minute infusion of ipilimumab and a 30-minute observation period (on Day 1 of each cycle only), followed by an approximately 30-minute infusion of BMS-986207 or its placebo. For participants < 22 kg, the infusion time for BMS-986207 600 mg or its placebo will be approximately 90 minutes.

There will be no intra-participant dose escalations or reductions of nivolumab or BMS-986207 or its placebo allowed. For Q3W dosing, participants may be dosed no less than 19 days from the previous dose. Premedications are not recommended for the first dose of study interventions.

Monitor participants carefully for infusion reactions during study intervention administration. If an acute infusion reaction is noted, manage participants according to [Section 7.4.4](#).

Doses of study drug(s) may be interrupted, delayed, skipped, or discontinued depending on how well the participant tolerates the treatment (see [Section 7.4](#)). Day 1 dosing visits for each cycle are not skipped.

Care must be taken to assure sterility of the prepared solution as the product does not contain any antimicrobial preservative or bacteriostatic agents.

Use separate infusion bags and filters when administering nivolumab, ipilimumab or BMS-986207 on the same day.

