7.4.2 Criteria to Resume Treatment

Participants may resume treatment with study intervention if they have completed AE management (ie, corticosteroid taper) or are on ≤ 10 mg prednisone or equivalent, and meet the requirements per [Table 7.4.2-1](#).

Prior to re-initiating treatment in a participant with a dosing delay lasting > 8 weeks, the Sponsor/Medical Monitor (or designee) must be consulted and treatment decision agreed upon. Continue tumor assessments per protocol even if dosing is delayed. Continue periodic study visits to assess safety and laboratory studies every 3 weeks or more frequently if clinically indicated during such dosing delays.

When criteria to resume treatment are met, resume all study interventions (BMS-986207 or its placebo, nivolumab and ipilimumab) on the same day unless the investigator determines that one of the agents must be discontinued due to toxicity attributed to that agent alone. Since this study is blinded, criteria for dose delay, resumption, and discontinuation in [Table 7.4.2-1](#) for BMS-986207 or its placebo will be the same as that for nivolumab. Thus, if nivolumab is resumed, BMS-986207 or its placebo will also resume. Treatment with BMS-986207 or its placebo will not resume without nivolumab.

Dose delay is required for participants with confirmed SARS-CoV-2 infection. Participants with confirmed SARS-CoV-2 infection may resume treatment after 1) at least 10 days (20 days for severe/critical illness) have passed since symptoms first appeared, positive RT-PCR test result, or positive viral antigen test result, 2) resolution of acute symptoms (including at least 24 hours has passed since last fever without fever reducing medications), 3) evaluation by the Investigator with confirmation that there are no sequelae that would place the participant at a higher risk of receiving investigational treatment, and 4) consultation by the Sponsor/Medical Monitor (or designee). For suspected cases, treatment may also resume if SARS-CoV-2 infection is ruled-out and other criteria to resume treatment are met.

Prior to re-initiating on-study intervention in a participant with a dosing delay lasting > 8 weeks due to SARS-CoV-2 infection, the Sponsor/Medical Monitor (or designee) must be consulted.

Table 7.4.2-1: Adverse Event Criteria for Delay, Resume, and Discontinue of Nivolumab, Ipilimumab, and BMS-986207

Drug-Related AE per CTCAE V5	Severity	Action Taken	Clarifications, Exceptions, and Resume Criteria

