9.1.2 Clinical Outcomes Assessments

The evaluation of PROs is an increasingly important aspect of clinical efficacy and safety in oncology trials. Such data provide an understanding of the impact of treatment from the participant's perspective and offer insights into participant experience that may not be captured through physician reporting.

Participants will be asked to complete the NSCLC-SAQ, the FACT-G7, the 5 Level EQ-5D Questionnaire (EQ-5D-5L), the PGIS and the PGIC at designated study visits. When possible, participants should complete the PRO measures prior to any other study related procedure or assessments during study visits. Assessments will be completed prior to dosing on Day 1 of each cycle from Cycle 1 (with the exception of the PGIC which will be completed at each cycle from Cycle 2; see Section 2 Schedule of Activities). PRO measures will be completed electronically during the study and at Safety and Survival Follow-up.

The PROs should be completed in the following order:

- 1) NSCLC-SAQ
- 2) FACT-G7
- 3) EQ-5D-5L
- 4) PGIS
- 5) PGIC (except for C1D1 when it is not completed)

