9.1.2.1 NSCLC-SAQ

The NSCLC-SAQ is a 7-item PRO measure intended for use in advanced NSCLC clinical trials to support medical product labelling.³⁷ The NSCLC-SAQ uses a 7-day recall period and verbal rating scale. It was developed in accordance with the US FDA PRO Guidance and scientific best practices, and the resulting qualitative interview data provide evidence of content validity. The NSCLC-SAQ total score measures overall severity of the following NSCLC symptoms: cough, pain, dyspnea, fatigue, and appetite. The NSCLC-SAQ has been qualified for exploratory use to measure symptoms of NSCLC in drug development programs. Further evaluation is needed on the instrument's longitudinal measurement properties and the interpretation of clinically meaningful within-patient change in score. After the NSCLC-SAQ's longitudinal measurement properties and the interpretation of clinically meaningful within-patient change have been evaluated, the NSCLC SAQ total score is intended to support labeling claims related to change in overall symptoms of NSCLC.

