NSCLC-SAQ total score and FACT-G7	Mean change from baseline in NSCLC-SAQ total score and FACT-G7 by treatment arm	Time from randomization until death, loss to follow-up, withdrawal of consent, or conclusion of the study, whichever comes first, for a period of up to 4 years from randomization.
EQ-5D-5L utility index and EQ VAS scores	Mean change from baseline in EQ-5D-5L utility index and EQ VAS scores by treatment arm	Time from randomization until death, loss to follow-up, withdrawal of consent, or conclusion of the study, whichever comes first, for a period of up to 4 years from randomization.

Abbreviations: ADA, anti-drug antibody; AE, adverse event; Ceoi, end of infusion concentration; Ctrough, observed serum trough concentration; EQ VAS, EuroQol visual analog scale; FACT-G7, Functional Assessment of Cancer Therapy - General - 7 item version; NSCLC-SAQ, Non Small Cell Lung Cancer Symptom Assessment Questionnaire; ORR, objective response rate; PGIC, Patient Global Impression of Change; PGIS, Patient Global Impression of Severity; PK, pharmacokinetic.

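### On-treatment questionnaires move with a delayed dose, so in participants who are delayed for toxicity and then resume, symptoms and quality of life are usually recorded after the episode rather than during it

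*Combined protocol and SAP*

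**What the plan says.** Three pieces of text fix when the questionnaires are completed.

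- **Table 2-2, Clinical Outcomes Assessments notes:** "Completed electronically prior to dosing on Day 1 of each cycle from Cycle 1 and then every cycle thereafter". A parallel note starts the PGIC at Cycle 2.
- **Section 9.1.2:** "Assessments will be completed prior to dosing on Day 1 of each cycle from Cycle 1", again with the PGIC from Cycle 2.
- **Table 2-2, footnote a:** if a dose is delayed, "the procedures schedule for that same time point must also be delayed to coincide with when that time" point's dose is given, "with the exception of tumor assessments which must occur as scheduled".

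Section 7.1 adds that "Day 1 dosing visits for each cycle are not skipped", so a Day 1 that cannot go ahead is deferred, and its questionnaires with it. For the period of a delay, Section 7.4.2 says: "Continue periodic study visits to assess safety and laboratory studies every 3 weeks or more frequently if clinically indicated during such dosing delays". It names no questionnaire.

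On recall, Section 9.1.2.1 states that "The NSCLC-SAQ uses a 7-day recall period and verbal rating scale". Section 9.1.2.2 gives 1 week for the FACT-G7, and Section 9.1.2.4 gives 7 days for the PGIS.

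Table 10.4.4-1 lists the output as "Mean change from baseline in NSCLC-SAQ total score and FACT-G7 by treatment arm", with similar summaries for the EQ-5D-5L and for the anchor-based NSCLC-SAQ work. It states no rule for assigning a deferred form to a time point.

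**The concern.** Under these rules, whether a form is completed during a toxic episode depends on whether the toxicity holds up dosing. Table 7.4.2-1 withholds all agents for many Grade 2 events. It lets dosing resume mostly at baseline or Grade 1, or for some events once they are controlled or reduced. The questionnaire waits for the same condition.

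The quantity at stake is the by-arm mean change in symptoms and quality of life while on treatment. Section 9.1.2 justifies collecting these data because physician reporting may miss what patients experience, so adverse event collection is not a full substitute. Section 3.3.1 says BMS-986207 could intensify immune-mediated events caused by the other two agents. If that leads to more delays in Arm A, the missing weeks fall more heavily on that arm. In addition, a form labelled Cycle 2 can belong to quite different calendar weeks in different participants.

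**Working it through.** The documents give no figure for this point (no questionnaire sample size, SD, delay rate or margin), so there is nothing to reproduce. Two calculations show the scale.

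**1. Interval between on-treatment forms**

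Inputs:
- Cycle of 6 weeks, with doses on Day 1 and Day 22, so 3 weeks between doses (Table 2-2).
- Discontinuation trigger at more than 8 weeks from the previous dose (Sections 8.1 and 8.1.1). There are exceptions for prolonged steroid tapers and for approved delays unrelated to drug.
- Assumption: a delayed Day 22 dose carries the next Day 1 with it. Visit windows are ignored.

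Formula: interval = (Day 1 to Day 22 gap) + (Day 22 to next Day 1 gap). A dose at the limit is 8 − 3 = 5 weeks past due.

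| Situation | Interval (weeks) | Share covered by a 7-day recall |
|---|---|---|
| As planned | 3 + 3 = 6 | 1/6 = 17% |
| One dose at the 8-week limit | 3 + 8 = 11 | 1/11 = 9% |
| Both doses at the limit | 8 + 8 = 16 | 1/16 = 6% |

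Under the steroid-taper exception the interval can be longer still.

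Example (the 3-week delay is assumed): a participant has Grade 2 diarrhea when Cycle 2 Day 1 falls due at week 6. Dosing resumes 3 weeks later, at week 6 + 3 = 9. The FACT-G7 completed then asks about weeks 8 to 9. No form is due at week 6, and none describes weeks 6 to 8.

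**2. Possible effect on the by-arm mean at one time point**

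Formula: hidden difference = (pA − pB) × d. Here pA and pB are the shares of each arm in a toxicity delay at that time point, and d is the worsening during toxicity that goes unrecorded. The documents give none of these, so all are assumptions.

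- In SD units, with an excess of 5 to 15 percentage points in Arm A and d from 0.3 to 0.8 SD: 0.05 × 0.3 = 0.015 SD, up to 0.15 × 0.8 = 0.12 SD.
- On the FACT-G7 total, range 0 to 28 (7 items scored 0 to 4), with d = 5 points: (0.20 − 0.10) × 5 = 0.5 points, or (0.30 − 0.10) × 5 = 1.0 point.

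Both treat d as wholly lost. Where the recall week still catches the tail of the episode, the effect is smaller for the same inputs.

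**The case against.** The strongest opposing case is that most toxicity information survives and that these endpoints decide nothing. Much of it stands.

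- A reader might infer that symptoms are measured only after toxicity has resolved. The documents do not support that. Toxicity that causes no delay is recorded on schedule: in Table 7.4.2-1, Grade 2 fatigue is exempt and Grade 2 rash counts only above 30% body surface area. Some events need only be controlled or reduced before dosing resumes. Many of the most severe events lead to permanent discontinuation. Those participants complete forms at end of treatment, and the NSCLC-SAQ, FACT-G7 and EQ-5D-5L at about days 30, 60 and 100 (Table 2-3).
- A reader might infer that harm is hidden. Adverse events are collected continuously (Section 9.2.1), safety visits continue during delays, and Grade 3 to 4 related events have their own monitoring boundary (Section 10.5.1).
- A reader might infer that a delay of more than 7 days erases the whole episode. What counts is the time from recovery to the form, not the length of the delay. Section 7.4.1 calls for re-evaluation at least weekly, so a recent episode can still fall partly within recall. A slow steroid taper widens the gap.
- Not every delay means a worse score: some are triggered by laboratory values. The NSCLC-SAQ and PGIS ask about cancer symptoms, so diarrhea would register on them only indirectly.
- The endpoints are exploratory and descriptive, and the go criteria use PFS. No bias in the NSCLC-SAQ change threshold has been shown. Separate PRO analysis plans may specify how time points are handled.
- The marker for footnote a sits on the Cycle 1 header, where the only questionnaire visit is Day 1. The footnote's wording is general, however, and Section 9.1.2 ties the forms to dosing independently.

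What remains is the participant who is delayed and then resumes. The follow-up forms do not reach this group during the delay, Table 2-3 does not include the PGIS or PGIC at all, and no analysis plan can recover a form that was never completed.

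**Conclusion.** The point holds for participants whose dose is delayed for a drug-related event and who later resume. For them, questionnaire timing depends on toxicity. The form usually follows resolution or control of the event, short recall reaches at most its tail, and the interval can stretch from 6 to about 11 or 16 weeks. Those intervals rest on the 8-week limit counted from the previous dose and on Day 1 moving with a delayed Day 22.

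The direction by arm is conditional. If delays are more frequent in Arm A, its on-treatment burden would tend to be understated in the exploratory mean changes. The documents say only that potentiation is possible and give no delay rate by arm. The range of 0.015 to 0.12 SD (or 0.5 to 1.0 FACT-G7 point) is therefore an illustration and not an estimate. Adverse event tables and the primary PFS analysis are not affected. This is an inexpensive improvement in data collection, worth making because the missed observations cannot be reconstructed.

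**What to change.** 1. In footnote a of Table 2-2, extend the exception for tumor assessments to the Clinical Outcomes Assessments.
2. Amend both Table 2-2 notes (the shared note and the PGIC note) and Section 9.1.2. Questionnaires should be completed electronically every 6 weeks from Cycle 1 Day 1, with a window (for example ±7 days), whether or not a dose is given, and before dosing when one is given that day. The PGIC still starts at the second time point. Changing the footnote and Section 9.1.2 alone would leave the Table 2-2 notes in contradiction.
3. Analyse by week from Cycle 1 Day 1 rather than by cycle number. State how off-schedule forms are assigned, and report dose delays and questionnaire completion by arm.

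The cost is small. The forms are electronic, and visits every 3 weeks during a delay are already required. Imaging every 6 weeks for the first 48 weeks gives a contact near most early dates. The protocol already keeps imaging and pregnancy testing off the dosing calendar. The downside is that some questionnaires fall on non-dosing days and need a little more reminder work at sites.
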